After enrollment and consent, each patient will be randomized to either placebo or intervention group. 110 sealed envelopes randomizing patients to the exposure group A (monochromatic light) or bulb B (placebo) white light bulb with blue outer coating.

The machine used for the study will be the Drager Photo-Therapy 4000 currently in use through the NICU at Texas Children's Hospital. The bulb is the standard Drager approved Osram Dulux 18W/830 commercially available bulb. This bulb produced light of 450-470nm wavelength, well within the visible spectrum. The protective plexi shield will remain in place. The bulb for the placebo group contains white florescent bulbs Osram Dulux 18W/830 with a blue plastic covering that will produce light containing all wavelengths in the visible spectrum but will appear blue due to the outer cover. To ensure that this bulb does not produce any monochromatic light, a calibration meter, (Solarmeter Model 9.4 Blue Light Meter measuring 422-499nm with range from 0-199.9 mW/cm² Blue Light) will be used.

Patients will be evaluated for emergence delirium by two nurses blinded to the study arm.

Each patient will be given a study specific number for de-identification of data avoiding use of any identifiers (name, DOB, MRN, date of service etc.).

Anesthetic Description

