A standard and routine anesthetic will ensue for these patients in line with routine operative practices at Texas Children's Hospital, including an inhalational induction (mask) using sevoflurane 8%v/v with oxygen/nitrous oxide 3/7 L/min respectively, followed by intravenous cannula placement. Propofol will be administered if needed to facilitate oral endotracheal intubation at the discretion of the anesthesia attending. Dexamethasone (0.5mg/kg), ondansetron (0.1mg/kg) and morphine (0.1-0.2mg/kg) will be administered for anti-inflammatory, antiemetic and analgesic effects respectively. Intravenous fluid (lactated ringer solution) will be continuously infused with the appropriate volume to be determined by the anesthesia provider. Maintenance of anesthesia will be with sevoflurane with the concentration titrated to maintain an appropriate level of hypnosis as determined by the anesthesia provider. At the conclusion of the surgery, the patient will undergo routine deep extubation according to the routine practice of the anesthesia providers of record. On arrival to the PACU, the Drager phototherapy lamp will be illuminated over the patient's head and neck. Randomization will determine if the patient will be exposed to ML blue light or the placebo bulb (white bulb with blue over coating). The PACU staff and the anesthesiologist will be blinded to study arm. The placebo bulb will provide blue light of all wavelengths as to not compromise blinding. The light will remain active and over the patient until the patient has been in the post anesthesia recovery unit (PACU) for 30 minutes.

Postoperative evaluation for emergence delirium

Two PACU nurses blinded to the patient group will be asked to complete the PAED scoring scale for evaluation of emergence delirium. They will be asked to complete the scoring evaluation upon arrival to the PACU and at 10 minutes, 20 minutes and 30 minutes following arrival. Two nursing evaluations will be used to reduce inter-observer bias. A patient

experiencing emergence delirium will receive standard pharmacologic treatment as determined by the anesthesiology provider irrespective of study participation. Blinding of the nurse and anesthesia team will help to ensure that the nursing staff will call the anesthesia providers with any and all usual questions and the anesthesia provider to react and treat potential ED as per usual practice without being biased by the study.

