The study will end at this point without the need for additional follow-up or patient contact related to the study.

Statistical Analysis Plan

Sample size/Data Analysis:

The PAED behavioral scale will be used to assess the incidence of emergence delirium. The PAED scale is a reliable tool to measure ED and involves five items: eye contact, purposeful actions, awareness of the surroundings, restlessness, and inconsolability. While other scales exist, the PAED scale is the standard for assessment of ED and is the only validated scale. A PAED score of >12 will be used to define ED.

Cohort means and standard deviations (SD) or counts and frequencies as appropriate for the variables collected. We will compare the blue light and Sham groups using the Student's t-test for continuous variables (e.g., age, PAED score) and the chi-square test for categorical variables (e.g. % female, ASA category). For counts < 5, the Fisher's exact test will be used. For baseline comparisons, absolute standardized differences instead of p-values will be used to compare the groups.

Given the prospective collection of data, missing data for the PAED scores over time indicated a patient woke up or experienced emergence delirium and so no imputation will be performed. To adjust for any remaining confounding among the variables collected, a logistic regression model with the outcome being emergence delirium and a second logistic regression model with the outcome being either ED or the patient had a PAED score of 12 or more at time periods 10, 20, and 30 min. Both regression models used as independent predictors the following variables: treatment group, age, weight, gender, and ASA category. Robust standard errors were derived to account for any within-cluster correlation at the individual nurse level given the possible serial correlation of outcomes within each nurse caring for his or her patients.

An a priori calculation of sample size was done using an incidence of 40% of emergence delirium in similar patient population. We assumed an absolute reduction of 25% (ie, 40% to 15%) in incidence of emergence delirium to be clinically significant. To detect this difference at 80% power with a two-sided alpha of 0.05, required a sample size of 98 participants.

All p-values < 0.05 were considered statistically significant.

Risk/Discomfort:

The study procedure poses no additional risk to patients. The major risk is loss of confidentiality.

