Use of monochromatic light has been safely tested in numerous human studies and used routinely in the NICU without identified patient risk using the same Drager machines at TCH. The moment the patient is awake and making purposeful eye contact with the PACU RN, the lights will be terminated. The risk of phototherapy is well known from nearly 40 years of clinical use in neonates. The risk of phototherapy is predominantly in neonates, especially preterm infants with jaundice, all requiring prolonged and continuous exposure to high intensity light for many days. This study will not include any neonates (with immature retina) or long term exposure of >30 min. The study will be terminated the moment the patient is awake and making purposeful eye contact with the PACU RN to avoid unnecessary discomfort.

Benefits:

The study benefits include improved understanding of emergence delirium and potential for both reduction in the incidence of emergence delirium and the use of pharmacologic agents.

Consent procedures:

The parental or legal guardian permission form will be signed prior to the beginning of surgery.

Confidentiality:

Personal Health Information(PHI) will be safeguarded at all times. Patients will be assigned a study ID number; their name or other identifying information will not be used in any presentations or publications resulting from this research. Data will be kept in a locked office to which only departmental personnel have access. Data files will be stored on a secure hospital network drive.

Sample collection:

Patients will be enrolled prospectively and randomized to either study or placebo arms. In addition, each patient will be assigned a random non-identifiable study number to ensure anonymity.

The following information will be recorded:

Age in months, gender, duration of procedure, duration from induction to extubation, Recovery time (defined as arrival in PACU to first spontaneous eye opening or response to verbal command)

PAED behavioral scoring sheet will be completed at: (T=0 on PACU arrival, 10, 20 and 30 minutes post PACU arrival). Nurse determination of occurrence of ED.

Administration of supplemental dexmedetomidine, propofol, opioid or benzodiazepine in PACU will be noted if given. Opioid given to treat pain will be noted as such.

References:

Sikich N, Lerman J: Development and psychometric evaluation of the Pediatric Anesthesia Emergence Delirium Scale. *Anesthesiology* 2004; 100:1138-45.

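### The emergence delirium (ED) endpoint has no time window, so a PAED score above 12 at PACU arrival, with essentially no light exposure, counts as an event

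*Combined protocol and SAP*

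**What the plan says.** - **Exposure.** Under Anesthetic Description: "On arrival to the PACU, the Drager phototherapy lamp will be illuminated". The procedure text describes no earlier exposure.
- **Scoring.** Under Sample collection: "PAED behavioral scoring sheet will be completed at: (T=0 on PACU arrival, 10, 20 and 30 minutes post PACU arrival". The section on postoperative evaluation gives the same four times. Neither section says whether the lamp or the first score comes first.
- **Definition.** Under Sample size/Data Analysis in the Statistical Analysis Plan: "A PAED score of >12 will be used to define ED". No time point is included or excluded.
- **Models.** The first logistic model has ED as its outcome. The second has either ED or "a PAED score of 12 or more at time periods 10, 20, and 30 min". Only that added criterion names time points, and it leaves out T=0. (Its cut-off also differs from the definition, which is a separate matter.)
- **A second record.** Sample collection also lists a nurse's determination of whether ED occurred, with no time window. The plan does not say whether this or the PAED score supplies the ED variable.
- **Sample size.** The calculation takes 40% ED without the intervention and treats a fall to 15% as the effect worth detecting. Its result is: "To detect this difference at 80% power with a two-sided alpha of 0.05, required a sample size of 98 participants".

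**The concern.** The primary aim is to learn whether the light lowers the incidence of ED. A child already above 12 when the lamp goes on is a case that the lamp had no opportunity to prevent. Read as written, the plan still counts that child as an event, both in the first logistic model and in the ED half of the second. The time limit in the second model does not help, because its outcome is met by either component.

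Two things are at stake. Events that the treatment cannot influence pull the risk ratio toward 1 and add variance, so the trial would have less power than it could have from the same children. And an unstated window leaves the choice of time points open until the data have been seen.

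**Working it through.** **Inputs from the Statistical Analysis Plan:** sham ED 40%, blue-light ED 15%, two-sided alpha 0.05, power 80%, total N 98. **Assumed:** 1:1 allocation, since the plan says only "each patient will be randomized to either placebo or intervention group".

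**Step 1: reproduce the plan's figure.** With the pooled-variance formula for two proportions and a mean rate of (0.40 + 0.15)/2 = 0.275:

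n per arm = [1.960 × √(2 × 0.275 × 0.725) + 0.8416 × √(0.40 × 0.60 + 0.15 × 0.85)]² / 0.25² = (1.2377 + 0.5102)² / 0.0625 = 48.9, rounded up to 49.

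The total is 98, as stated. Power at 49 per arm is 80.1% by the normal approximation and 80.9% by exact enumeration of the chi-square test. Exact values are used below unless noted.

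**Step 2: put a T=0 rate into the model.** Let q be the share of children in each arm who exceed 12 at T=0. It is equal in both arms because the lamp has not yet had time to act. Hold total sham ED at 40%, and apply the planned risk ratio, 0.15/0.40 = 0.375 (a 62.5% reduction), to post-arrival events only.

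- T=0 counted: sham 0.40; blue q + 0.375 × (0.40 − q).
- T=0 not counted, all children kept: sham 0.40 − q; blue 0.375 × (0.40 − q).

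The difference is 0.625 × (0.40 − q) either way.

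| q | Counted: sham vs blue | Risk ratio | Power | Not counted: sham vs blue | Risk ratio | Power | Difference, both ways |
|---|---|---|---|---|---|---|---|
| 0 | 40.0 vs 15.0% | 0.375 | 80.9% | 40.0 vs 15.0% | 0.375 | 80.9% | 25.0 points |
| 2.5% | 40.0 vs 16.6% | 0.41 | 74.5% | 37.5 vs 14.1% | 0.375 | 77.4% | 23.4 points |
| 5% | 40.0 vs 18.1% | 0.45 | 67.4% | 35.0 vs 13.1% | 0.375 | 73.5% | 21.9 points |
| 10% | 40.0 vs 21.3% | 0.53 | 52.3% | 30.0 vs 11.3% | 0.375 | 65.2% | 18.8 points |

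**Step 3: separate the two sources of loss.** Not counting T=0 events recovers 77.4 − 74.5 = 2.9, 73.5 − 67.4 = 6.1 and 65.2 − 52.3 = 12.9 points, so about 3, 6 and 13. The rest of the fall from 80.9% arises because fewer of the 40% are preventable, and no choice of window restores it. The recoverable part is a matter of variance. At q = 5%, for example, the standard error of the difference is √[(0.40 × 0.60 + 0.18125 × 0.81875)/49] = 0.089 with T=0 counted and √[(0.35 × 0.65 + 0.13125 × 0.86875)/49] = 0.083 without, for the same 21.9-point difference.

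**Step 4: vary the model.** If T=0 events instead came on top of the planned rates (42.5 vs 17.5%, 45 vs 20%, 50 vs 25%), the difference would stay at 25 points and power would be 78%, 76% and 73%. By the normal approximation, if 10%, 20% or 30% of sham events fell at T=0 within the 40% (q = 4%, 8%, 12%), power would be 70%, 58% and 46% counted against 74%, 67% and 60% not counted.

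**Limit of the calculation.** The not-counted figures treat T=0 cases as having no later score above 12. A child still above 12 at 10 minutes counts under either definition, so the gain would then be smaller.

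**The case against.** **The T=0 rate may be close to zero.** Children are extubated deep, and recovery time is recorded from PACU arrival to first eye opening, so waking is expected after arrival. This stands. The documents give no rate, the 10% row has no support in them, and at zero the issue has no effect.

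**The planned 40% to 15% may already describe all counted ED.** If so, power is 80% with T=0 included and nothing is lost. This also stands as a reading. The losses above depend on confining the effect to post-arrival events, which is an assumption of this check.

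**A reader might infer that T=0 is scored before any light.** The documents do not say so, because lamp and score are both placed at arrival in no stated order. They support only that exposure is nil or nearly nil. The Purpose section also speaks of perioperative exposure and the Background of light in the operating room, whereas the procedure starts it in the PACU. Those passages must be reconciled.

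**A reader might infer that counting T=0 events shrinks the observed difference and explains the whole fall from 81% to 52%.** It does not. At a given T=0 rate the difference is the same either way, and most of the fall remains after T=0 is left out.

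**ED may be taken from the nurse's determination instead.** That is possible, but that record has no window either, so the gap remains.

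**Conclusion.** The point holds in a limited form. As written, a T=0 score above 12 is an ED event although essentially no light exposure preceded it. Any such events dilute the risk ratio and add variance.

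The avoidable cost is the gap between counting and not counting them: about 3, 6 or 13 points of power at T=0 rates of 2.5%, 5% or 10%. This assumes 49 per arm, a 40% sham total, equal T=0 rates in both arms, and a 62.5% reduction confined to later events.

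It would be wrong to conclude that the trial is biased toward a false positive. Events occurring equally in both arms do not raise type I error, and their effect is conservative. Nor do the documents show that power is in fact below 80%, since the T=0 rate is not given. The change is still worth making because it uses scores already planned and fixes the window before the data are seen.

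**What to change.** In the Statistical Analysis Plan:

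1. Define primary ED as a PAED score above 12 at 10, 20 or 30 minutes, and use that variable wherever ED is an outcome.
2. Keep every randomized child in the denominator. Treat T=0 as a baseline score and report T=0 cases by arm.
3. State the order of lamp switch-on and T=0 score.
4. State whether the PAED score or the nurse's determination is the ED record.
5. Add two sensitivity analyses: count T=0 cases as ED, and exclude them from both arms.

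Exclusion belongs in a sensitivity analysis because it removes children after randomization, possibly after the lamp is on, and gains little: 78%, 74% and 67% power against 77%, 74% and 65% with everyone kept. Adding the T=0 score to the logistic model is also not advised as a default. The plan expects about 49 × 0.40 + 49 × 0.15 ≈ 27 events and already has five predictors.

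**Cost:** no new data, slightly fewer counted events, and children with ED only at T=0 become non-events. The plan treats missing later scores as a sign of waking or ED, so it should say explicitly how a T=0 case with no later score is classified.
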